We undertook a scoping review to inform our proposal and choice of primary outcome measures (DAMA, emergency readmission), searching MEDLINE and EMBASE (via Ovid) on 31/09/2020. We used search terms relating to three domains: OST; health care facility; and outcomes ["delay\* OR readmission\* OR discharge], excluding sources reporting on neonates [NOT neonat\*]. We searched from 1/01/2000 and only reviewed sources presenting empirical data. This resulted in less than 250 unique sources. Timely OST provision for hospital inpatients and at emergency and acute admissions was evidenced to reduce rates of self-discharge and emergency readmission [5, 6, 36, 40, 44-46]. Qualitative data highlighted how the distress of opioid withdrawal could result in self-discharge [2, 8, 9, 30] with case reports cautioning of "the potential morbidity of methadone treatment interruption in the hospital setting" [47]. This evidence strongly suggests that interventions to improve OST provision in hospitals will have an important impact on reducing DAMA.

Systematic review data indicate that 25-30% of PWUO leave hospital prior to completing medical treatment [40]. Patients who leave hospital prematurely are 12 times more likely to be readmitted with a related diagnosis within 14 days, and twice as likely to die [40, 48, 49]. This exacerbates health inequalities among a marginalised population, increases health care system burden and contributes to escalating economic costs [32, 33, 50]. Economic analysis show that the average costs associated with a readmission within 30-days of DAMA are estimated as 56% higher than the costs associated with completing the initial hospitalization [33].

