## FORMATIVE RESEARCH

Among 455 PWUO in London, we found that care delay was common and associated with bacterial infection severity and hospitalisation [1-3]. Inpatient hospitalisation for preventable bacterial infection was reported by 30% (137), of whom 40% (55) developed septicaemia and/or endocarditis [3]. A cycle of DAMA and emergency readmission was common. Primary reasons for DAMA were stigma and drug withdrawal due to delayed OST provision [2]. These are modifiable risk factors. Building on these findings, we requested substance dependence policies from all NHS hospital trusts (118 replied) and conducted workshops with PWUO, drug treatment service and hospital staff, to further understand this problem and identify solutions. We found:

- Poor information and care pathways between hospitals and community drug services.
- Inefficiencies in medicines reconciliation leading to delayed or omitted OST dosing.
- Limited knowledge among hospital staff about opioid withdrawal identification and management.
- Inconsistent substance dependency guidelines across hospital trusts: 59 (50%) stated they had no policy.
- A disempowered patient population, who report feeling unsafe in hospitals and lack advocacy support.

This proposal builds on these findings and aims to address the problems we have identified.

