## THE INTERVENTION

We regard iHOST as a structural intervention. That is, an intervention that promotes the availability, accessibility or acceptability of specific resources needed to improve health outcomes [62]. iHOST is purposefully designed to be pragmatic and practical within the real-world settings of hospital and drug treatment centres. The five iHOST components (My Meds card, hospital provider training, advocacy helpline, policy template and iHOST champion) have been co-produced. Their proposed relationship to short, medium- and long-term outcomes (figure 2) is informed by the team’s research, PPI consultation and evidence review.

Our scoping review identified procedural and attitudinal barriers to the effective management of opioid withdrawal in hospital, with medical professionals often displaying negative attitudes towards PWUO, which may impact the care they provide [31, 41]. In the short term, we anticipate the iHOST **training module** and **champion** will help to increase awareness of the importance of managing withdrawal and challenge stigmatising preconceptions held about PWUO, while the information fields on the **MY MEDS Card** (supplemented by **Helpline** guidance if required) will help remove procedural barriers to timely OST medicines reconciliation. Qualitative work has demonstrated that drug withdrawal, and fear of withdrawal is a key factor leading DAMA [2, 63, 64], which is associated with hospital readmission and increased mortality risk related to delays in treatment [[38, 65-68].

[figure not shown]

Figure 2: Working logic model

By improving the management of withdrawal and reducing delays in the prescription of OST we anticipate a reduction in DAMA, which will lead to decreasing re-admissions, morbidity, and mortality. Our London-based research with PWUO highlighted how fear of withdrawal informed delayed care seeking, leading to severe complications and hospitalisation [2, 3]. The **MY MEDS Card** and the **Advocacy Helpline** are informed by PPI and cultural safety principles [69, 70] with the aim of helping PWUO feel safer and more confident to seek timely medical care. In the longer term, we envisage that increasing awareness of changes in practice among the wider PWUO community related to iHOST will encourage patients to seek care earlier, leading to improved medical outcomes.

The iHOST intervention comprises:

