1. MY MEDS CARD

*“We need something like that [card] to take to the hospital to say I’ve got a right to be treated with dignity” (PWUO workshop participant, Care and Prevent Study, London 2019)*

The ‘My Meds’ card prototype (Figure 3) was co-produced in three London workshops with PWUO and refined in collaboration with hospital clinicians, pharmacy and drug treatment service providers. It is designed to be given to those on OST by their prescriber or drug treatment key worker. We have consulted drug treatment providers CGL, Turning Point, Humankind and NHS addiction services regarding implementation feasibility. Most already liaise with the social enterprise Exchange Supplies who will design, produce and distribute the finalised cards (optimisation, phase 1) to intervention site drug services.

Figure 3. My Meds Card prototype

The MY Meds card is credit card sized, double sided, and generic rather than personalised. **It aims to:**

- Empower people on OST to feel safe to access hospital care and to disclose their medication requirements.
- Enable timely medicines reconciliation: prescriber and pharmacist contacts to be entered by the drug service
- Support patients and staff with specialised OST advocacy and information (Release helpline).

No hospital will prescribe OST on the basis of the card alone. PWUO can choose to take or refuse a card (not mandatory).

The card was developed at the request of service users who valued the prospect of having physical ‘evidence’ of the right to treatment. On consultation we found that a digital record would be difficult for many to carry or access. This would also require data-harmonisation across multiple prescribing agencies, and data protection measures difficult to agree and complete within the scope of this project. We will scope potential for future digitisation to inform project recommendations (in line with the NHS Long Term Plan).

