## Analysis

### QUANTITATIVE EVALUATION

Our quantitative analysis of outcomes has two elements: (1) a detailed analysis of OST provision and patient outcomes before and after implementation of iHOST, using data extracted from local clinical systems at iHOST hospitals (i.e. an uncontrolled analysis) and covering all quantitative outcomes and (2) a controlled analysis of the two primary outcomes (DAMA and 28-day readmissions), comparing PWUO in the iHOST sites with other hospitals across England, using patient-level HES from NHS Digital. These two elements will both be implemented during the feasibility stage at UCLH and the formal evaluation at Leeds and Staffordshire hospitals. Depending on local data availability, there may be some differences in the definition of locally measured outcomes between iHOST sites.

**1. Detailed before/after analysis based on local data.** This will involve comparison of OST provision and outcomes before and after implementation of iHOST. We will derive patient-level data on each outcome and use regression to test whether there is a difference in the outcomes for patients admitted in the 12 months before the iHOST “go-live” date and those admitted in the 12 months after this date, adjusting for potential patient-level confounders such as the reason for admission. Outcomes will be grouped into: (a) patient outcomes in all those identified as PWUO; b) characteristics of OST prescribing in those receiving OST.

- a. **Patient outcomes in PWUO:** Based on phase 1 feasibility work a range of approaches will be used to identify PWUO in the participating hospitals including: free test records of OST prescriptions in the community, and diagnostic coded for opioid use those with opioid poisoning or injecting-related injuries. Outcomes will include receipt of OST during admission; DAMA; and 28-day emergency readmissions (all binary outcomes). The analysis will then use logistic regression to compare the probability of each outcome for this patient group in the 12 months before vs. the 12 months after the iHOST “go live” date.

Sensitivity analyses will use wash-out periods 3 months either side of the intervention, as there may be changes in practice in the run up to the start date and the intervention may take some time to embed.

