**2. Controlled analysis using HES (difference-in-difference [10]).** This analysis will involve measuring the change in primary outcomes at iHOST sites before and after iHOST implementation and comparing this change to other hospitals over the same time period. HES does not show whether patients received OST in hospital, and we will therefore need to identify a group of patients who may benefit from iHOST. Our planned inclusion criteria will be all admissions at acute hospital trusts in the 12 months before or after the iHOST “go-live” date, the patient is aged 18-64 at admission, and the patient has an ICD-10 diagnosis of opioid dependence (F11) in any diagnostic position, either in that admission or an admission at any hospital nationally in the previous 12 months. For each admission we will derive the two primary outcomes: DAMA and 28-day emergency readmission. We have previously used HES to measure these outcomes in comparable populations [32, 76] and are familiar with the structure of HES. We will then fit logistic regression models where the dependent variable is the outcome and the independent variables include an interaction term between the iHOST site status and whether the patient was admitted before or after iHOST implementation. We will also include patient-level confounding variables such as age, comorbidities, and the primary reason for admission, and a random intercept for the hospital site. This analysis addresses the question “did the risk of self-discharge/readmission reduce more at iHOST sites than at other hospitals”? Depending on the number of patients with admissions at the same hospital both before and after iHOST “go-live”, or at similar dates at iHOST sites and other hospitals, it may also be possible to conduct a sub-analysis of within-patient differences using conditional regression.

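### Cohort entry in the HES and local analyses rests partly on records that iHOST can plausibly increase at iHOST sites only, so the identified case-mix can shift after go-live and bias both primary outcomes in an unknown direction

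*Protocol*

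**What the plan says.** The Protocol (Analysis, Quantitative evaluation, item 2) sets the planned inclusion rule for the difference-in-difference on DAMA and 28-day emergency readmission: age 18-64, admitted within 12 months either side of go-live, and meeting this criterion: "ICD-10 diagnosis of opioid dependence (F11) in any diagnostic position, either in that admission or an admission at any hospital nationally", with a look-back of 12 months for the earlier admission. The code may therefore come from the admission being analysed. In the after period it may also come from an earlier admission that itself followed go-live.

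The local before/after analysis (item 1a) identifies its cohort from "free test records of OST prescriptions in the community, and diagnostic coded for opioid use", together with opioid poisoning and injecting-related injuries. Neither rule is limited to information recorded before exposure.

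On the intervention side, the My Meds card aims to "Empower people on OST to feel safe to access hospital care and to disclose their medication requirements" and to "Enable timely medicines reconciliation: prescriber and pharmacist contacts to be entered by the drug service". Formative Research lists "Limited knowledge among hospital staff about opioid withdrawal identification and management" among the problems the proposal addresses. The Intervention section adds that, in the longer term, awareness of iHOST "will encourage patients to seek care earlier, leading to improved medical outcomes".

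The HES model adjusts for variables such as age, comorbidities and primary reason for admission, with a random intercept for hospital. A within-patient analysis is described as possible, depending on numbers. Alternative patient groups are mentioned as a potential sensitivity analysis for local data. The Mixed Method Synthesis section considers differences in how DAMA, ward absences and inpatient drug use are recorded, but not differences in recording the opioid dependence or OST that defines the cohort.

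**The concern.** Whether an admission is counted depends in part on what is disclosed and written down during or after exposure to iHOST. If disclosure rises, free-text OST records rise almost directly and F11 coding plausibly rises too. This would happen at iHOST sites, after go-live, and not at comparators, which is the contrast that the interaction term estimates. Subtracting the comparator trend cannot separate a change in who is counted from a change in what happens to patients.

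If the added patients differ in DAMA or readmission risk from those identified before go-live, the estimate moves with no true effect. A 12-month national look-back brings in many patients regardless of iHOST, but it reaches past go-live as the after period advances. For an admission six months after go-live, half of the look-back already follows exposure. What is at stake is whether the primary difference-in-difference estimates can be read as effects of iHOST.

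**Working it through.** **Inputs from the Protocol**
- Baseline DAMA: "25-30% of PWUO leave hospital prior to completing medical treatment" (Background and Rationale). The Protocol does not say that this was the simulation input.
- Target effect and size: 250 patients per site for 80% power to detect a 33% reduction (Sampling and Recruitment).
- Volume: 400-500 PWUO admitted per site per year, so 800-1,000 per 12-month period over two sites, treated here as admissions.

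**Assumptions, not in the Protocol**
- g, the growth in the identified iHOST-site cohort caused by better capture.
- r, the DAMA risk in the added patients.
- Two-sided 5% test.
- 40,000 comparator admissions per period at 25% DAMA.
- No case-mix adjustment and no clustering.

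**The Protocol's own figure.** Baseline risk, alpha and the counting unit (per period or in total) are not given, so 250 per site cannot be strictly reproduced. A pooled two-proportion calculation with 2 × 250 = 500 per period gives 80.0% power at a 20% baseline, 89.5% at 25% and 95.2% at 30%. The figure is not shown to be wrong, and this point does not depend on it.

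**Bias with no true effect.** The after-period risk is p1 = (p0 + g·r)/(1 + g), and the spurious OR is [p1/(1 − p1)]/[p0/(1 − p0)]. With p0 = 25%:

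| g | r | p1 | Relative change | OR |
|---|---|---|---|---|
| 20% | 10% | (0.25 + 0.02)/1.2 = 22.5% | −10% | 0.87 |
| 20% | 25% | (0.25 + 0.05)/1.2 = 25.0% | 0 | 1.00 |
| 20% | 40% | (0.25 + 0.08)/1.2 = 27.5% | +10% | 1.14 |
| 10% | 10% | (0.25 + 0.01)/1.1 = 23.6% | −5.5% | 0.93 |
| 10% | 40% | (0.25 + 0.04)/1.1 = 26.4% | +5.5% | 1.07 |
| 30% | 5% | (0.25 + 0.015)/1.3 = 20.4% | −18% | 0.77 |
| 30% | 40% | (0.25 + 0.12)/1.3 = 28.5% | +14% | 1.19 |

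The 10% rows also show dilution by the look-back. If half the cohort qualified only on an index-admission code (assumed), a 20% rise in that half is 10% growth overall.

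**Chance of a false significant result** at g = 20%, with 900 admissions before and 900 × 1.2 = 1,080 after:
- r = 10%: the variance of the log OR is 1/(900 × 0.25 × 0.75) + 1/(1,080 × 0.225 × 0.775) + 2/(40,000 × 0.25 × 0.75) = 0.0115, so SE = 0.107. Then z = ln(0.871)/0.107 = −1.29, and P(significant fall) = Φ(−1.96 + 1.29) ≈ 25%.
- r = 40%: SE = 0.104 and z = ln(1.138)/0.104 = 1.24, so P(significant rise) = Φ(−1.96 + 1.24) ≈ 24%.
- The nominal value in each tail is 2.5%.

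**Power in a cohort defined by prior codes.** The number per period is n = [1.96√(2p̄(1 − p̄)) + 0.84√(p0(1 − p0) + p1(1 − p1))]²/(p0 − p1)², where p1 is now 0.67·p0 (a true 33% reduction) and p̄ is the mean of p0 and p1.
- 25% against 16.75%: about 380 per period over both sites; 380/800 = 47.5%, or about 48% of admissions.
- 30% against 20.1%: about 300 per period; 300/800 = 37.5%, or about 38%.

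The Protocol does not give the share of admissions with a qualifying prior code.

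**The case against.** The case for the plan has several parts, and much of it stands.

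- **The coding step is inferred.** A reader might infer that iHOST is designed to increase F11 coding. No section says so. The stated aims are disclosure, medicines reconciliation, awareness and better OST management. The card is optional, and training is voluntary except for champions, with 50% uptake expected. Case-mix can change; the Protocol does not show that it will.
- **The direction is open.** A reader might infer a bias in favour of iHOST, because cards go to people already on OST, who could be at lower risk. The Protocol's own account points the other way as well: it treats delayed or omitted OST as a driver of DAMA, so patients previously missed could be at higher risk. Adding them would mask a benefit.
- **Adjustment helps in part.** If added patients are admitted for unrelated reasons, primary reason for admission and comorbidities absorb some of the difference. The rejection rates above ignore this. No listed covariate records why the patient was identified, so adjustment is incomplete.
- **The look-back dilutes the effect.** Patients coded before go-live at any hospital enter regardless, and early after-period look-backs lie mostly before go-live.
- **Some mitigation is mentioned.** The within-patient analysis, the alternative patient groups and the option to refine the analysis plan after the systems reviews are real, but conditional. The wash-out sensitivity analysis does not help if recording stays changed.

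What remains is that a fixed inclusion rule for both primary outcomes depends on records that exposure can alter, and no firm part of the plan detects or bounds the result.

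**Conclusion.** The concern holds as a possible differential selection bias of unknown sign. With 25% baseline DAMA, no true effect and 20% growth in capture, the spurious odds ratio runs from 0.87 (10% DAMA in added patients) to 1.14 (40%). It is nearer 1 where most patients already have a prior code, and exactly 1 if the added patients carry the baseline risk. Growth in capture and risk in the added patients are both assumptions, and the calculation omits case-mix adjustment and clustering. The same mechanism applies to 28-day readmission, for which no figures were worked.

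The documents do not support the claim that DAMA will appear to fall, or that the planned cohort must be abandoned. Whether a prior-code cohort should be primary is a trade-off that turns on a share the Protocol does not report.

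**What to change.** 1. **HES analysis.** Pre-specify an analysis of both primary outcomes in a cohort defined only by F11 codes made before exposure, with equal look-backs counted from the first introduction of iHOST: months −24 to −13 for the before window and −12 to −1 for the after window. Report it beside the planned cohort.
2. **Choice of primary.** Before go-live, use HES to find the share of admissions with a qualifying prior code. Make the prior-code cohort primary only if that share keeps adequate power: about 48% at a 25% baseline or 38% at 30%, assuming 800 admissions per year.
3. **Capture check.** Report, by site group and period, the number and share of admissions that qualify only on an index-admission code, with a difference-in-difference on that capture. State in advance that a differential rise limits causal interpretation.
4. **Local cohort.** Report monthly capture by identification route. Repeat the analysis in patients found by routes less dependent on OST disclosure (opioid poisoning and injecting-related injury codes).

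**Cost.** This is analysis wording, with no HES data earlier than month −24, which the present look-back already needs. If go-live is dated after the three-month embedding period and not from first introduction, the extract starts up to three months earlier. The prior-code cohort is smaller and excludes first-time-coded patients, whom iHOST also serves. It does not remove a case-mix change that comes from earlier care seeking.

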## DESIGN

We employ a quasi-experimental design. Our primary outcomes will be measured through a difference-in-difference analysis [10] of routinely collected clinical data at two iHOST evaluation sites. We will measure the

difference in primary outcomes at iHOST sites compared to the difference at other hospitals in the national database, controlling for patient-level and hospital-level confounders. In-depth qualitative interviews and focus groups will be conducted with staff and PWUO exposed to the intervention for a process evaluation of iHOST acceptability, barriers, and enablers.

Following consideration of a number of experimental designs, including cluster randomised designs, step-wedge trials, and individually randomised trials, we do not plan to conduct a randomised controlled trial of iHOST. This is because we aim to understand the best way to improve access to an evidence-based intervention (OST) in hospitals, and are seeking to generate practical (or ‘realist’) information about programme design rather than the most robust possible estimate of the effect of the intervention on patient outcomes. Additionally, after discussion with partners, we felt an individually-randomised trial would be unfeasible as the intervention works at hospital-level, and cluster-randomised designs would require substantially more hospital sites to achieve reasonable power.

[figure not shown]

Figure 1: iHOST Phases and Participant Flow

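### The HES difference-in-difference model gives no variance to a hospital's own change between years, so with two treated hospitals its standard errors are too small whenever hospitals drift differently

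*Protocol*

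**What the plan says.** All references are to the Protocol.

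- **Treated units.** Under Design, the primary outcomes come from "routinely collected clinical data at two iHOST evaluation sites". Quantitative Evaluation says that the same controlled analysis will also be run at the feasibility stage for UCLH, which is one treated hospital.
- **Effect term.** Quantitative Evaluation, item 2, tests "an interaction term between the iHOST site status and whether the patient was admitted before or after iHOST implementation".
- **Dependence structure.** The same item lists patient-level confounders such as age, comorbidities and "the primary reason for admission, and a random intercept for the hospital site". It names no hospital-by-period term, no other variance method and no patient-level term.
- **Rows.** "Our planned inclusion criteria will be all admissions at acute hospital trusts in the 12 months before or after" go-live, and "For each admission we will derive the two primary outcomes: DAMA and 28-day emergency readmission". Repeat patients appear only in an optional extra: "it may also be possible to conduct a sub-analysis of within-patient differences using conditional regression".
- **Level of the intervention.** Design rejects randomisation partly because "the intervention works at hospital-level, and cluster-randomised designs would require substantially more hospital sites to achieve reasonable power".
- **Power.** Sampling and Recruitment reports a simulation: about 250 patients per intervention site for 80% power to detect a 33% reduction in self-discharge, with 400-500 PWUO expected per site per year.

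**The concern.** In a before/after comparison, a hospital's random intercept cancels. What remains is that hospital's change between the two years. It contains the intervention effect, sampling noise, and whatever else changed there, such as staffing, coding or ward organisation. The stated model has a variance for the sampling noise and none for the last part. Drift at the two treated hospitals is then read as intervention effect, with a standard error that assumes no drift.

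The protocol itself expects something of this kind. Mixed Method Synthesis plans to use interviews and observation to pick up changes over time at the intervention sites, and site differences in how staff record DAMA. Design uses the hospital-level nature of the intervention as an argument about power. Choosing not to randomise does not remove that source of variance.

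The analysis concerns both primary outcomes, its results feed the cost-effectiveness analysis, and national roll-out is the anticipated consequence of a positive result.

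**Working it through.** **1. The protocol's own figure.** Sampling and Recruitment gives neither the baseline risk nor alpha behind the 250 per site, and does not say whether its simulation allowed for hospital drift. The figure therefore cannot be reproduced from stated inputs alone. A plain two-proportion calculation with independent rows comes close under one assumption. With p1 = 0.20 (assumed), p2 = 0.67 × 0.20 = 0.134, mean 0.167, two-sided 5%:

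n per period = [1.96 √(2 × 0.167 × 0.833) + 0.842 √(0.160 + 0.116)]² / 0.066² ≈ 500,

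which is about 250 per site per period over two sites. At the 25-30% DAMA rate cited in Background and Rationale, 500 per period gives about 90-95% power, and 250 per period about 62-73%.

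**2. Inputs for the error rate.**
- From the protocol: two treated hospitals; one 12-month block each side of go-live; DAMA 25-30%; 400-500 PWUO per site per year.
- Assumed: n = 450 rows per treated hospital per period (the protocol counts people, not admissions); J = 120 comparator hospitals; two-sided 5%; a 15% baseline as a lower bound; and τ, the SD of a hospital's log-odds in each period around its own mean, from 0 to 0.20.

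**3. Formulas.** With v = 1 / [n p(1 − p)]:

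- SE assumed by the model = √[2v(1/2 + 1/J)]
- true SE = √[2(v + τ²)(1/2 + 1/J)]
- ratio r = √[(v + τ²)/v]; actual type I error = 2[1 − Φ(1.96 / r)]
- SD of a hospital's year-on-year change in risk ≈ √2 × τ × p(1 − p)

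The formula uses equal hospital sizes. J cancels from r, so the assumed number of comparators hardly matters.

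**4. Worked at p = 0.25, n = 450.** v = 1/(450 × 0.1875) = 0.01185; model SE = √(0.01185 × 1.0167) = 0.110.

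| τ | SD of yearly change | True SE | r | Type I error, p = 0.25 | Range, p = 0.15 to 0.30 |
|---|---|---|---|---|---|
| 0.05 | 1.3 points | 0.121 | 1.10 | 7.5% | 6.7-7.8% |
| 0.10 | 2.7 points | 0.149 | 1.36 | 14.9% | 11.8-16.0% |
| 0.20 | 5.3 points | 0.230 | 2.09 | 34.9% | 28.0-37.0% |

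**5. Simulation of the stated model** (logistic, hospital random intercept, site-by-period interaction, 1,000 runs per setting, comparators of 80-449 rows). At τ = 0, 0.10 and 0.20 the rejection rates were 4.9%, 14.9% and 33.6% at a 25% baseline, and 3.4%, 12.9% and 32.2% at 15%. At 25% and τ = 0.20 the mean model SE was 0.112, against a true SD of 0.234.

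**6. More rows do not help.** With 250 rows per site per period the formula gives 8.8-11.2% at τ = 0.10 and 19-27% at τ = 0.20, both lower than with 450. As n grows, v shrinks and τ² does not.

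**7. Repeat admissions, simulated separately** (mean 1.5-3 admissions per patient, patient SD 0.7-1.5, no hospital drift). The error rate is about 5-6% when each patient's admissions fall at random over both periods, and 6-18% when they all fall in one period.

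**The case against.** The strongest reply is that the size of the problem depends wholly on τ, which the protocol does not give. With τ = 0.05 the test is only mildly liberal. Design also promises adjustment for hospital-level as well as patient-level confounders, so the relevant τ is what is left after adjustment. The covariate list is open-ended, a SAP may add detail, and the protocol allows the analysis plan to be refined. Design further says that the study does not seek the most robust possible effect estimate, and no alpha or decision rule is stated.

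Much of this stands as a limit on magnitude. It does not repair the model. The random-effects structure is stated, not left open, and covariates cannot be assumed to absorb all hospital-specific change at two sites. Qualitative insight into site changes helps interpretation but adds no width to an interval.

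A reader might infer three stronger things:

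- That the p-values are known to be far too small. The documents do not support this, because the drift is not given and the result runs from near-nominal to severe.
- That repeat admissions are an equal fault. They are secondary, since their effect largely cancels when a patient's admissions span both periods.
- That the local before/after models ignore repeat admissions in the same way. Item 1 speaks of patient-level data and does not fix admissions as rows.

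**Conclusion.** The point holds in conditional form. As written, the primary controlled model sets hospital-by-period variance to zero while two hospitals (one for UCLH) carry the effect, so its standard errors are too small whenever hospitals drift differently. For DAMA at 450 rows per site per period, type I error is about 7-8% at τ = 0.05, 12-16% at 0.10 and 28-37% at 0.20. The middle value needs a year-on-year change with an SD of only about 2.7 percentage points at a 25% baseline. These figures rest on the assumed τ and row count. Readmission was not calculated; the direction is the same, the size unknown.

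**What to change.** In Quantitative Evaluation, item 2, add a hospital-by-period random effect, estimated from the comparator hospitals, and base confidence intervals and p-values for both primary outcomes on it. In simulation (450 rows per treated site per period, 4,000 runs per setting, τ from 0 to 0.3), analysing hospital-level changes with this variance estimated from the comparators brought type I error back to about 4-6.5%.

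Support it with a placebo (permutation) comparison of the two-site change against comparator hospitals. This should allow for hospital size, because smaller comparators have noisier changes. The placebo test was not simulated here, so it is proposed as support and not as the sole test. Ordinary cluster-robust standard errors should not be relied on with two treated clusters.

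As a secondary change, allow for several admissions by one patient, through a patient-level term or patient-level clustering.

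No new data are needed. The cost is wider intervals and lower power. For a 33% reduction at a 25% baseline and 450 rows per site per period, simulated power is about 99% with no drift, 90% at τ = 0.10 and 59% at τ = 0.20; at a 15% baseline it is 86%, 74% and 46%. The 80% power statement in Sampling and Recruitment should be rechecked under the corrected model, with its baseline risk and assumed drift stated, and restated if needed. Drift can be estimated from comparator hospitals in HES years before go-live, without sight of the intervention results.
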